
Endpoint Category	Estimand			
	Endpoint(s)	Population	Intercurrent event(s) handling strategy and missing data handling	Population-level summary
			
analysis (treatment policy); otherwise, for travel \geq 42 consecutive days, a hypothetical strategy will be used where data during patient travel will be set to missing
 
In addition, the missing data imputation rules for patients who have no available values of CSMS⁴ during the last 12 weeks of the treatment period are as follows:
 
 Missing data due to patients' discontinuation from study due to AEs and lack of efficacy will be imputed using worst average CSMS score during the last 12 weeks of all observations in the corresponding treatment group Missing data due to any other reason will be imputed using MI 	

[1] If a data point or missing value falls into multiple categories of intercurrent events as specified above, the following priority order for handling of data will be applied: ICE 3), ICE 4), ICE 5b) ICE 5a), ICE 1), ICE 2). For example, if data or missing value fall into both ICE 3) and 5a), the strategy for ICE 3) should be followed, as it takes priority over 5a).
 
[2] Select prohibited medications that will be handled using a treatment policy are listed in Category 1 of Table 7
 
[3] Additional prohibited medications listed in Category 2 Table 7 will undergo blinded adjudicated by study medical monitor before the database lock to determine if they will be handled by treatment policy, composite strategy, or hypothetical strategy
 
[4] No available values of CSMS means no available TNSS, TOSS, or DMS during the last 12 weeks of the efficacy assessment period
				

The primary analysis will focus on the comparison between REGN1908-1909 and placebo in the FAS. The analysis will be performed using an analysis of covariance (ANCOVA) model, with the treatment group, randomization stratification factors (as stratified), and cat sIgE (<17.5 kUa/L versus ≥ 17.5 kUa/L) as fixed effects and the baseline CSMS as a covariate. The baseline CSMS will be calculated as the average CSMS during the first 15 consecutive days of the baseline assessment period where eligibility criteria (for TSS and rescue medication use) were met, as specified based on the following two criteria:

1. Must have at least 8 unique days of a TSS score ≥ 8 within a 15 consecutive day period.

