2. Must have a least 8 unique days of a DMS score >0 within the same 15 consecutive day period as Criteria 1. The 8 unique days do not have to occur on the same days as Criteria 1; however, they must be within the same 15 consecutive days.

If less than 15 days of data are available during the baseline assessment period, the baseline will be the average CSMS over all available days (if duplicate entries of CSMS are available on the same day, the worst score will be used).

Only days with observed data will be included in the calculation of average score. The average CSMS (max score 38/day) will be calculated based on the sum of average daily TNSS (max score 12/day), average daily TOSS (max score 6/day) and average daily medication scores (DMS, max of 20/day) recorded over the last 12 weeks of the treatment period (weeks 48 to 60).

For the MI procedure, missing data (the average CSMS) will be imputed 50 times to generate 50 complete data sets utilizing the SAS procedure PROC MI. Note that any imputation by worst CSMS score as specified in [Table 4](#) will occur prior to MI. The 2 steps below will be followed for MI:

Step 1: The Markov Chain Monte Carlo (MCMC) method will be used to fill in missing values of average CSMS during weeks 0-12 by treatment group so that a monotone missing pattern will be formed.

Step 2: Using the data sets from Step 1, missing values of average CSMS from weeks 48-60 will be imputed using a monotone regression method. The imputation model will include the covariates in the ANCOVA model and the average CSMS from weeks 0-12.

For steps 1 and 2, any score imputed outside the range of CSMS (0-38) will be truncated to the nearest value of CSMS according to the following algorithm:

- If the imputed score > 38, then the final imputed score will be 38.
- If the imputed score < 0, then the final imputed score will be 0.

Sample SAS syntax code for MI:

```
proc mi data=mi1 out=mi3 noint nimate=50 seed=190819;
mcmc impute=monotone;
var BASELINE CSMS012 CSMS4860;
by TRTP;
run;

proc mi data=mi3 out=mi4 nimate=1 seed=190819;
class TRTP STRAT1 STRAT2 STRAT3 CATIGE;
monotone reg;
var TRTP STRAT1 STRAT2 STRAT3 CATIGE BASELINE CSMS012;
by _imputation_;
run;
```

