5.6.2. Analysis of Secondary Efficacy Variables

The secondary efficacy endpoints will be analyzed using an ANCOVA model in the same fashion as the primary analysis of the primary endpoint.

Average Daily Symptom Score Endpoints (TOSS, TNSS, DMS, TSS)

The average TOSS, TNSS, and DMS will be calculated using all observed daily scores during the specified time period (initial 12 weeks or last 12 weeks of the treatment period).

The average TSS will be calculated by adding average TNSS and average TOSS during the specified time period (initial 12 weeks or the last 12 weeks of the study).

The intercurrent events, strategies, and the corresponding missing data handling approaches for these endpoints will follow the same strategy as for the primary endpoint, outlined in [Table 4](#).

Supplemental analyses using non-parametric methods, such as Wilcoxon ranked sum test or Hodges-Lehmann analysis of median differences, may be performed in the event of a violation of the normality assumption.

Asthma-related endpoints (ADSS, FEV1, ACQ-5)

All asthma endpoints will be analyzed on patients in the FAS with asthma (all randomized patients with ongoing asthma in medical history). Supplemental analyses may be performed in the subset of ongoing asthma patients who were also on asthma medication at baseline.

All available daily ADSS will be averaged over the specified time period (initial 12 weeks or last 12 weeks of the treatment period). If ADSD or ANSD is missing on any given day, ADSS score for that day will be considered missing and no value will be calculated. In addition, ANSD will be shifted by one day, i.e., ADSD on Day 1 and ANSD on Day 2 will be used to get the ADSS on Day 1, ADSD on Day 2 and ANSD on Day 3 will be used to get the ADSS on Day 2, and so on. The day before Visit 6 or Visit 14 for the initial 12 weeks and last 12 weeks, respectively, will be the last day that contributes to the average ADSS (since there will generally be no ANSD measurement corresponding to the date of Visit 6 or 14).

The estimand for ADSS will follow the same approach as for the primary endpoint, described in [Table 4](#). Separate analyses of average ADSD and average ANSD may also be performed.

Estimands for FEV1 and ACQ-5 are specified in [Table 5](#). A supplemental analysis may be performed for the change from baseline ACQ-5 endpoint only in patients with baseline ACQ-5 > 1.5.

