5.6.3. Adjustment for Multiple Comparisons

A non-binding futility interim analysis (IA) is planned in this study (details are provided in Section 7) and an administrative penalty of 0.001 will be taken from the significance level used at final analysis, and thus 2-sided 0.049 will be used. No further multiplicity adjustment will be performed for the IA.

The following multiplicity adjustment approach, a hierarchical procedure, will be used to control the overall Type-1 error rate at 0.049 for the primary endpoint and the secondary endpoints of R1908-1909 versus placebo. Each hypothesis will be formally tested only if the preceding one is significant at the 2-sided 0.049 significance level. The hierarchical testing order is shown in below table (all comparisons are with the placebo).

Level	Endpoints	Testing Order
Primary endpoint	Daily CSMS, averaged over the last 12 weeks of the treatment period (weeks 48 to 60)	1
Secondary endpoints	Daily TNSS, averaged over the last 12 weeks of treatment period (weeks 48 to 60)	2
	Percent change from baseline to the end of treatment (week 60) in cat SPT mean wheal diameter	3
	Percent change from pre-treatment baseline in average TNSS, over the last 12 weeks of the treatment period (weeks 48 to 60)	4
	Daily CSMS, averaged over the initial 12 weeks of the treatment period (weeks 0 to 12)	5
	Daily TNSS, averaged over the initial 12 weeks of treatment period (weeks 0 to 12)	6
	Daily TSS, averaged over the last 12 weeks of the treatment period (weeks 48 to 60)	7
	Daily TSS, averaged over the initial 12 weeks of the treatment period (weeks 0 to 12)	8
	Percent change from pre-treatment baseline in average CSMS, over the last 12 weeks of the treatment period (weeks 48 to 60)	9
	Change from baseline to week 60 in RQLQ(S)+12	10
	DMS, averaged over the last 12 weeks of the treatment period (weeks 48 to 60)	11
	Daily TOSS, averaged over the last 12 weeks of the treatment period (weeks 48 to 60)	12
	Percent change from pre-treatment baseline in average TSS, over the last 12 weeks of the treatment period (weeks 48 to 60)	13

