6.1. Definition of Baseline for Efficacy/Safety Variables

Unless otherwise specified, the Baseline assessment for all measurements will be the latest available valid measurement taken prior to the first administration of study drug. If any randomized patients are not treated, the baseline will be the last value on or prior to the randomization. The following rules specify the determination of baseline by both date/time information:

- For the AE, lab, PK and ADA data, both date and time of the measurement will be used to determine baseline by comparing with the first injection date and time.
- For other data except AE, lab, PK or ADA, only date of the measurement will be used to determine baseline by comparing with the first injection date.

For the rescreened patients, all data from the same patient will be used to derive baseline regardless if the data is from the screen-failure subject ID or enrolled subject ID.

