6.2. Data Handling Conventions

For the laboratory safety variables and biomarker data, if the data are below the lower limit of quantification (LLOQ)/limit of linearity, half the lower limit value (i.e., LLOQ/2) will be used for quantitative analyses. For data above the upper limit of quantification (ULOQ)/ limit of linearity, the upper limit value (i.e., ULOQ) will be used for quantitative analyses.

For efficacy endpoints defined as percent change from baseline, if both baseline and post-baseline values are 0s, the percent change from baseline will be 0; if baseline value is 0 and post-baseline value is a positive number, the percent change from baseline will be assigned by 100%. Missing baseline values for efficacy endpoints will be imputed using the average baseline value across all patients.

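### Only CSMS has a written 15-day baseline; by default TNSS, TSS and the other diary scores fall back to one diary day, which matters mainly for percent change in TNSS (order 4) and TSS (order 13)

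*SAP*

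**What the plan says.** SAP 6.1 sets the default: unless otherwise specified, "the Baseline assessment for all measurements will be the latest available valid measurement taken prior to the first administration of study drug". For data other than AE, laboratory, PK and ADA data, "only date of the measurement will be used to determine baseline by comparing with the first injection date".

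SAP 5.6.1 overrides the default for one diary score: "The baseline CSMS will be calculated as the average CSMS during the first 15 consecutive days of the baseline assessment period" in which the TSS and rescue-use entry criteria were met. If fewer than 15 days exist, "the baseline will be the average CSMS over all available days".

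For the component scores SAP 5.6.2 says "The average TOSS, TNSS, and DMS will be calculated using all observed daily scores during the specified time period", and it limits that period to the initial or last 12 weeks. TSS and ADSS are handled in the same on-treatment terms. The covariate for these endpoints is named only as the matching baseline value (SAP 10.1.1). SAP 4.1 lists baseline TNSS, TOSS, TSS and DMS without defining them.

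In the hierarchy of SAP 5.6.3, order 4 is "Percent change from pre-treatment baseline in average TNSS, over the last 12 weeks of the treatment period (weeks 48 to 60"), and order 13 is the same quantity for TSS. SAP 6.2 adds that "if baseline value is 0 and post-baseline value is a positive number, the percent change from baseline will be assigned by 100" percent.

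**The concern.** On the literal text, percent change in TNSS and TSS divides a 12-week mean by one evening's diary entry. The error in that single entry sits in the denominator, so it inflates the spread of the ratio. The covariate adjustment cannot remove it.

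Order 4 is the fourth gate of a fixed sequence. If it fails, orders 5 to 13 are not formally tested, and these include CSMS over the initial 12 weeks and RQLQ(S). Order 13 is last, so its failure blocks nothing else.

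There is also a coherence problem. With one-day component baselines, baseline TSS plus baseline DMS will generally not equal baseline CSMS. Two programmers could reasonably derive different baselines for an endpoint that carries alpha.

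A smaller timing gap sits beside this. Symptom scores are entered at bedtime and compared with the injection by date only. SAP 6.1 does not say how an entry on the evening of the first injection, made after dosing, is to be treated. SAP 6.5 counts that date in the initial 12 weeks.

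**Working it through.** **1. The plan's own figures.** Inputs from SAP 2.3: difference 1.8, SD 6.2, two-sided alpha 0.049, power 90%. With n = 2(z₁₋α/₂ + z₁₋β)²σ²/δ², n = 2 × (1.9685 + 1.2816)² × 6.2²/1.8² = 250.6, so 251 per arm. The exact t-test gives 252 (power 89.9% at 251), and 252/0.8 = 315. At 315 and 251 per arm, TNSS power (0.7, SD 2.3) is 96.8% and 92.4%; TSS power (0.8, SD 3.0) is 91.5% and 84.5%. These agree with SAP Table 1 (96/92 and 91/84). The plan states no precision for any percent-change endpoint.

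**2. Error in one day against 15 days.** With independent days, the within-patient error SD of one day is √15 = 3.9 times that of a 15-day mean. With day-to-day autocorrelation 0.5 the ratio is 2.3, and with 0.8 it is 1.5.

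**3. What the entry criteria guarantee.** A patient who meets both criteria has TSS of at least 8 on 8 of 15 days, so the 15-day mean TSS is at least 8 × 8/15 = 4.3. TOSS is capped at 6, so TNSS is at least 2 on those days and its mean is at least 8 × 2/15 = 1.1. Mean DMS is above 0. A 15-day baseline therefore cannot be zero for TNSS, TSS or DMS in such a patient. A one-day baseline can. For DMS, up to 7 of the 15 days (47%) may be zero, although percent change in DMS carries no alpha.

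**4. Effect on order 4.** The documents give no day-to-day SD, baseline mean or baseline-to-outcome correlation, so all are assumed: baseline TNSS mean 6 or 7, between-patient SD 1.5, autocorrelation 0 or 0.5, correlation 0.3 or 0.6, and a proxy for the entry criterion. The simulation used 251 per arm, alpha 0.049, and ANCOVA on treatment and baseline.

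| Day-to-day SD | Rise in residual SD of percent change | Power, 15-day | Power, one day |
|---|---|---|---|
| 1.0 | 6-15% | 97-99% | 96-98% |
| 1.5 | 16-32% | 96-99% | 90-97% |
| 2.0 | 36-57% | 97-99% | 85-90% |

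One cell by hand (mean 6, day-to-day SD 2.0, independent days, correlation 0.3):
- 15-day baseline: difference 10.73 points, residual SD 30.21. Then 10.73/(30.21 × √(2/251)) = 3.98 and Φ(3.98 − 1.97) = 0.98.
- One-day baseline: difference 12.34, residual SD 45.04. The ratio is 3.07 and Φ(3.07 − 1.97) = 0.86.

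A second set of assumptions (mean 6.5, between-patient SD 2.0, outcome SD 2.3, difference 0.66, correlation 0.6, entry criterion applied, 400 trials per setting) gave one-day power of about 93%, 84% and 74% at day-to-day SD 1.3, 2.0 and 2.5, each within about 2 points. The 15-day figure for that model, run without the entry criterion, was about 95-96%.

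**5. Zero baselines for TNSS.** At most 0.4% in the first set. In the second, 0, 0.25% and 0.9%.

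**6. Absolute TNSS.** Moving from a 15-day to a one-day covariate cost at most about 2 power points in the first set.

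**The case against.** The strongest reply is that a one-day baseline was never meant. SAP 5.6.2 opens by saying the secondary endpoints follow the primary ANCOVA approach, and the 15-day baseline is defined within that approach. Average CSMS is itself built from average TNSS, TOSS and DMS. The protocol collects all these scores over the same 15-day period. This stands as evidence of intent, so a reader should not infer that the SAP has deliberately chosen one day. But the sentence concerns the model and does not mention baseline, while SAP 6.1 states an operative default. Intent is not a derivation rule.

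Three other inferences are tempting and not supported:

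- *Every percent-change test in the hierarchy is degraded.* CSMS (order 9) has its 15-day rule, and SPT (order 3) is a clinic measurement for which the last value is ordinary. For the absolute scores (orders 2, 6, 7, 8, 11 and 12) baseline is only a covariate. The SAP's stated power comes from an unadjusted t-test, so a noisier covariate gives up part of an unplanned gain.
- *The baseline window of study day 1 or earlier admits the Day 1 evening entry.* SAP 6.5 excludes daily diary data from those visit windows. Only the silence of the date-only rule remains.
- *The zero-baseline rule threatens order 4.* Once the entry criterion is applied, zero TNSS baselines are under about 1%.

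**Conclusion.** The point holds as an unwritten baseline that defaults to one diary day, and it is worth correcting before unblinding. The textual gap needs no assumption. The direction of the effect is also secure: one day is a noisier denominator than a 15-day mean.

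The size is not secure. It depends on a day-to-day SD, a baseline mean and a correlation that the documents do not give. Over the assumed range, order-4 power falls by a point or two when daily scores are steady and by roughly ten points when the day-to-day SD is 2.0. A figure near 74% needs an SD of 2.5, which is extreme. Power levels also shift with the assumed effect and correlation, so they illustrate the loss and do not bound it. Order 13 is exposed in the same way but was not simulated. For absolute scores the loss is small.

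**What to change.** Add two sentences to SAP 6.1 or 5.6.2:

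1. Baseline for TNSS, TOSS, TSS, DMS, ADSS, nighttime awakenings and asthma rescue use is the average over the same 15 consecutive days used for baseline CSMS, or over all available days if fewer than 15.
2. No diary entry dated on or after the first injection date counts towards baseline.

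Because SAP 5.6.2 pairs each day's ADSD with the next morning's ANSD, the second sentence drops at most one ADSS day, and only when the window runs up to the injection date. The protocol already requires at least 15 consecutive days of these entries, so the cost is SAP text and programming. No new data are needed.

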6.2. Data Handling Conventions

For the laboratory safety variables and biomarker data, if the data are below the lower limit of quantification (LLOQ)/limit of linearity, half the lower limit value (i.e., LLOQ/2) will be used for quantitative analyses. For data above the upper limit of quantification (ULOQ)/ limit of linearity, the upper limit value (i.e., ULOQ) will be used for quantitative analyses.

For efficacy endpoints defined as percent change from baseline, if both baseline and post-baseline values are 0s, the percent change from baseline will be 0; if baseline value is 0 and post-baseline value is a positive number, the percent change from baseline will be assigned by 100%. Missing baseline values for efficacy endpoints will be imputed using the average baseline value across all patients.

6.3. Data Handling Convention for Spirometry Data

This applies to the selection of the FEV1 and FVC values to be used in analysis. As part of a central OverRead review, the best FEV1 value and best FVC value will be identified from multiple spirometry efforts performed at the same time. Additionally, spirometry measures will be classified during the OverRead as Acceptable, Borderline Acceptable or Unacceptable.

In the event that the best value at the baseline visit is graded as Unacceptable, the best spirometry effort from a prior screening visit that is graded as Acceptable or Borderline Acceptable should be considered the baseline value. If all available values prior to first administration of study drug are graded as Unacceptable, the baseline value should be set to missing.

Similarly, for post-baseline visits, if all available values are graded as Unacceptable, the data from that visit should be set to missing. Otherwise, the best value should be used in the case of multiple efforts performed at the same time.

6.4. Data Handling Convention for Missing Data

Missing data will not be imputed in listings. This section includes the methods for missing data imputation for some summary analyses, if necessary.

Rules for handling missing data for primary and secondary efficacy variables are described in Section 5.6.1 and Section 5.6.2.

Adverse event

If the intensity of a TEAE is missing, it will be classified as “severe” in the frequency tables by intensity of TEAEs. If the assessment of relationship of a TEAE to the investigational product is missing, it will be classified as related to the investigational product.

Adverse event start date

AE start date will be used for AE classification and analysis of AESIs. If AE start date is not complete, then the character variable will keep the original incomplete date, the numerical date variable will be imputed, and an imputation flag will be used to indicate which date component is missing.

If AE start day is missing, and AE start month and year are not missing: If AE start year is the same as first dose year and AE start month is the same as first dose month, then AE start day will be imputed using the day of first dose. If this leads to a date after the AE end date, AE end date will be used instead. If AE start year is the same as first dose year and AE start month different from first dose month, AE start day will be imputed using the first day of the month. If this leads to a date before informed consent date, the informed consent date will be used. Imputation flag is ‘D’.

If AE start month is missing, and AE start year is not missing: If AE start year is before the first dose year, the informed consent day and month will be used. If AE start year is the same as first dose year, the first dose day and month will be used. If this leads to a date after AE end date, AE end date will be used instead. If AE start year is after the first dose year, January 1st will be used. Imputation flag is ‘M’.

If AE start year is missing: The date of first dose will be used. If this leads to a date after the AE end date, AE end date will be used instead. Imputation flag is ‘Y’.

Adverse event end date

The general recommendation is not to impute AE end date. However, since AE end date will be used for AE start date imputation, to carry through the logic for programming, the following intermediate step will be used. Afterwards, only the original character/numeric date recorded in CRF will be kept in the final analysis dataset.

If AE end day is missing, and AE end month and year are not missing: AE end date will be imputed using the last day of the month. If this leads to a date after end of study follow up date, the end of follow up date will be used instead.

If AE end month is missing, and AE end year is not missing: AE end date will be imputed using December 31st as the day and month. If this leads to a date after end of study follow up date, the end of follow up date will be used instead.

If AE end year is missing: AE end date will be imputed using end of follow up date.

Medication start and end date missing

To determine whether a medication is prior medication or concomitant medication or both, the missing medication start date is estimated as early as possible, and the missing medication end date is estimated as late as possible. If the medication start date is missing, the onset day will not be calculated in medication listing.

Prior medication start date

If start day is missing, and start month and year are not missing: the start day will be imputed using the first day of the month. Imputation flag is 'D'.

If start month is missing, and start year is not missing: the day and month will be imputed using January 1st. Imputation flag is 'M'.

If start year is missing: the start date will be imputed using 2 years before informed consent date. Imputation flag is 'Y'.

A special note: for start date with year missing, the general principle is not to impute. However, to simplify the programming flow, the imputation is proposed to align with protocol which specifies to collect up to 2 years prior medication. Since the start date of prior medication will not be used in any analysis, the rule will not impact the analysis result.

Prior medication end date

If end day is missing, and end month and year are not missing: the end date will be imputed using the last day of the month. If this leads to a date on or after first dose intake date, the first dose intake date – 1 will be used. Imputation flag is 'D'.

If end month is missing, and end year is not missing: the end date will be imputed using December 31st as the day and month. If this leads to a date on or after first dose intake date, the first dose intake date – 1 will be used instead. Imputation flag is 'M'.

If end year is missing: the end date will be imputed using the first dose intake date – 1. Imputation flag is 'Y'.

Concomitant medication start date

The imputation rule for concomitant medication start date is the same as AE start date.

Concomitant medication end date

If end day is missing, and end month and year are not missing: the end date will be imputed using the last day of the month. If this leads to a date after end of study follow up date, the end of follow up date will be used. Imputation flag is 'D'.

If end month is missing, and end year is not missing: the end date will be imputed using December 31st as the day and month. If this leads to a date after end of study follow up date, the end of follow up date will be used instead. Imputation flag is 'M'.

If end year is missing: the end date will be imputed using the end of follow up date. Imputation flag is 'Y'.

Medication coding

Medications whose ATC level 4 cannot be coded will be summarized by setting ATC4=ATC2 in the table programs. However, these uncoded ATC level 4 records still need to be confirmed with study data manager and study medical director.

PCSV

Subjects who had post-baseline PCSV but missing baseline value will be regarded as having treatment-emergent PCSV.

